### *Milk test*

During the week before the milk test, subjects will fill a food diary. Moreover they will be instructed to not drink any milk, dairy product and any food product containing milk proteins during the 2 days before the milk test. On the day of the milk test, fasting subjects will fill out questionnaires about their actual appetite and GI symptoms, baseline urine and blood samples will be collected, and fasting glycaemia by finger-prick will be measured (time 0). Subsequently, subjects will drink 250 ml of milk within 10 min and thereafter, glycaemia, symptoms and appetite questionnaires, as well as blood samples and urine will be collected at specific time points (time 0.5, 1, 2, 4 and 6 hours after milk ingestion). After the last blood drawing, subjects will be offered lunch and, before leaving the study centre, they will be instructed to fill out GI symptoms and appetite questionnaires, to collect urine, to

fill out a 1-day food diary, and to consume a fixed dinner. Questionnaires, diaries and 6-24h urine samples will be delivered to the laboratory on the next day.

Blood samples will be centrifuged at 4°C and 4000 rpm; serum, plasma and plasma + aprotinin samples will be aliquoted and stored at -40°C.

Plasma samples will be analyzed for:

- casein digestion-derived peptides (beta-casomorphins and all known peptides derived from milk proteins);
- aminoacid profile;
- endocannabinoids and N-acyl-ethanolamines (ECs).

Plasma samples added with aprotinin will be analyzed for:

- gastro-intestinal hormones (in plasma samples pre-treated with aprotinin): insulin, GIP, GLP-1, glucagon, c-peptide, ghrelin, leptin.

Serum samples will be analyzed for:

- DPPIV activity;
- baseline DPPIV concentration.

In urine samples, aliquoted (1.5 ml) and frozen at -40°C, all the following analytes will be measured:

- lactose excretion levels;
- galactose + glucose excretion levels;
- indican excretion levels;
- baseline creatinine concentration.

Subjects will be also asked to collect a fecal sample under usual dietary habits and to fill out questionnaires as follows:

- physical activity questionnaire (short version of the IPAQ);
- questionnaire on quality of life;
- questionnaire on depression, anxiety and stress (DASS);
- semi-quantitative food frequency questionnaire (FFQ);
- the King's Stool Chart, to evaluate frequency and consistency of feces;
- Three Factor Eating Questionnaire (TFEQ) to evaluate individual eating behaviour.

Anthropometric data of weight and height will be measured as well.

Fecal samples, stored at -40°C, will be used for DNA extraction according to the standard operating procedures of the International Human Microbiome Consortium (<http://www.human-microbiome.org/>). Statistical analysis will be carried out by the most appropriate methods in order to infer the associations between specific microbiota signatures and clinical, dietary and metabolomic variables.

## Statistical analysis plan

### Sample size calculation

The sample size for this study has been calculated on the basis of the primary endpoints here listed:

- milk-derived peptides plasma concentrations after milk consumption;
- lactose urinary excretion after milk consumption;
- post-prandial plasma profile of GI hormones and ECs.

Considering circulating mean values and standard deviations reported by Deth et al. (2016) in blood of healthy population, power analysis indicated that a sample size of 19 participants per group is sufficient to detect a minimum variation of 40% in circulating BCM-7 with a power of 80% and an  $\alpha = 0.05$ .

Considering excreted % of lactose in urine, hydrogen concentration in breath and relative standard deviations as reported by Bezerra et al. (1990) a sample size of 19 participants per group is sufficient to detect a 15% minimum variation of lactose and a 50% minimum variation of hydrogen in healthy subjects, with a power of 80% and an  $\alpha = 0.05$ .

Regarding post-prandial plasma profile of GI hormones and ECs, our previous studies showed that a sample size of 13 participants is adequate to find significant differences with an 80% power and an  $\alpha = 0.05$ . (Mennella et al., 2015; Mennella et al., 2016).

The participant number will be increased up to 40 (20 subjects per group) in view of possible dropouts.

### Statistical analysis

Data will be expressed as means  $\pm$  SEMs, unless otherwise specified.

Two-tailed P values lower than 0.05 were considered significantly different

Missing data will be handled as such, i.e., no imputation of missing data will be performed.

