## **Objectives**

This study aims to compare two groups of healthy (non-lactose intolerant) subjects who are irregular milk consumers, due to milk induced gastrointestinal disorders, with another group of healthy subjects who consume milk regularly, without symptoms, in relation to the primary and secondary objectives here described.

By performing a milk test in which volunteers ingest 250 ml of UHT semi-skimmed milk, primary objectives include the evaluation of:

- plasmatic response of milk-derived peptides;
- plasmatic profile of GI hormones;
- plasmatic profile of endocannabinoids and N-acyl-ethanolamines.
- urinary profile of lactose over 24 h;

Secondary objectives include the assessment of:

- baseline and postprandial plasma profile of aminoacids;
- baseline and postprandial blood glucose;
- baseline and postprandial GI symptoms;
- baseline serum concentration of dipeptidyl peptidase IV (DPPIV);
- baseline and postprandial serum activity of dipeptidyl peptidase IV (DPPIV);
- urinary excretion of indican as marker of protein digestibility;
- correlations of GI symptoms with appetite ratings and blood glucose, plasma GI hormones, plasma peptides and amino acids as well as with urinary excretion of lactose and galactose + glucose;
- the composition of the intestinal microbiota (metagenomic analysis);
- the psychological profile through questionnaires on the perception of quality of life, on levels of depression, anxiety and stress and on eating behavior.

Further secondary objectives include the assessment of:

- the prevalence of lactose malabsorption in the two groups, by using results from Lactose H2 breath test performed during the recruitment procedure;
- urinary excretion of lactulose, mannitol and sucralose as markers of intestinal permeability after an oral challenge of these 3 sugar probes.

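### At least 11 unranked primary analytes are each tested at P<0.05, with no lead endpoint and no adjustment stated across analytes

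*Combined protocol and SAP*

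**What the plan says.** - **Threshold.** Statistical analysis gives a single rule without exceptions: "Two-tailed P values lower than 0.05 were considered significantly different".
- **Primary content.** Objectives lists four primary items: milk-derived peptides, GI hormones, endocannabinoids with N-acyl-ethanolamines, and "urinary profile of lactose over 24 h". Sample size calculation states "The sample size for this study has been calculated on the basis of the primary endpoints here listed" and gives the same content in three bullets, with hormones and endocannabinoids merged. Neither list has an order or a lead.
- **Analytes.** Milk test names seven hormones ("insulin, GIP, GLP-1, glucagon, c-peptide, ghrelin, leptin"), urinary lactose, two endocannabinoid classes whose members are not named, and a peptide panel described as "beta-casomorphins and all known peptides derived from milk proteins".
- **Power.** 19 per group is called "sufficient to detect a minimum variation of 40% in circulating BCM-7 with a power of 80" per cent. The same 19 is given for urinary lactose. For hormones and endocannabinoids, "a sample size of 13 participants is adequate to find significant differences with an 80% power". Every statement uses alpha 0.05.
- **Adjustment.** Continuous variables with repeated measures attaches a Bonferroni adjustment to the repeated-measures ANOVA of normally distributed variables. No adjustment is stated for Friedman/Wilcoxon, for the between-group AUC comparisons, or for the Spearman correlations with species and gene abundances. PLS-DA is named without any validation step.

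**The concern.** The endpoints are called primary and the trial was sized on them, yet nothing says which result carries the conclusion about habitual versus non-habitual milk consumers. If no analyte truly differs, there is still an appreciable chance that at least one is reported as a group difference. A finding picked out after the data are seen could not then be told apart from one planned in advance. How many tests there are depends partly on how many peptides the assay reports.

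Two related gaps sit in the secondary analyses. About 5% of truly null microbiota correlations would be called significant. With 20 subjects per group and many features, PLS-DA can also show separation by overfitting, and no check on this is named.

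**Working it through.** **1. Counting the analytes (Milk test).** 7 hormones + 1 urinary lactose + beta-casomorphins, endocannabinoids and N-acyl-ethanolamines counted once each = 7 + 1 + 3 = 11. This is a floor: class members are not named, and the peptide list is open-ended.

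**2. The plan's own sample size.** The 19 per group cannot be reproduced, because the means and SDs are only cited. Solving a two-sided two-sample t test backwards (19 per group, alpha 0.05, power 80%) gives a standardised difference d = 0.934. For a 40% change in BCM-7 this implies a coefficient of variation of 0.40/0.934 = 43%. It assumes that 19 is the smallest adequate number for the endpoint.

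**3. Chance of at least one false positive.** One between-group test per item and no true differences. Under independence the formula is 1 − 0.95^k. The correlated figures come from simulating equally correlated normal statistics (400,000 draws). The correlations are assumptions, since the documents give none.

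| Tests k | Independent | Correlation 0.3 | 0.5 | 0.8 | Expected false positives (0.05k) |
|---|---|---|---|---|---|
| 3 | 14.3% | 13.7% | 12.6% | 9.8% | 0.15 |
| 4 | 18.5% | 17.4% | 15.6% | 11.4% | 0.20 |
| 11 | 43.1% | 37.4% | 30.3% | 17.9% | 0.55 |

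Several analyses per analyte (time points, AUC, quartiles) would raise these figures.

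**4. What an equal alpha split would do to power (d = 0.934).**

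| Alpha | 19 per group | 20 per group |
|---|---|---|
| 0.05 (lead endpoint) | 80.0% | 82.1% |
| 0.05/3 = 0.0167 | 64.4% | 67.3% |
| 0.05/4 = 0.0125 | 60.1% | 63.1% |

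Restoring 80% at 0.0125 would take 28 per group. A prespecified lead endpoint keeps the planned power without more subjects.

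**5. Power per analyte under Benjamini-Hochberg, q = 0.05.** Simulated independent t tests at 19 to 20 per group.

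| Family | Assumed d | Truly different | Power |
|---|---|---|---|
| 9-10 analytes (lactose if not lead, hormones, endocannabinoids) | 0.934 | 1 | 47-52% |
| 10 analytes | 0.934 | 8 | 73-76% |
| 10 analytes | 1.145 | 1 | 71-74% |
| 30 peptides | 0.934 | 1 | 33-36% |
| 60 peptides | 0.934 | 1 | 26-28% |
| 110 peptides | 0.934 | 1 | 20-22% |

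The value d = 1.145 applies if the 13 participants quoted for hormones and endocannabinoids means 13 per group, which the plan does not say. The peptide-family sizes are assumptions.

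**6. Error left after the change.** With no true differences and independence, two families give 1 − 0.95² = 9.8%. A lead endpoint plus two families gives 1 − 0.95³ = 14.3%.

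**The case against.** The strongest case against has five parts.

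- **The plan does adjust.** This is true for the repeated-measures ANOVA, so a reader who infers that there is no multiplicity control at all goes too far. The adjustment is not stated to reach across analytes or to the other tests.
- **Familywise control is a judgement in a small comparison of two consumer groups.** This stands, which is why declaring no confirmatory claim is an acceptable answer. The documents do not make that declaration: they call the endpoints primary and size the trial on them.
- **The remedy still leaves about 14%, the same as three unadjusted endpoints.** The arithmetic is right. The gain is at analyte level, against 43% for 11 independent analytes (18-37% at the assumed correlations), and the lead endpoint is itself held at 5%.
- **The power loss rests on an unseen effect size.** This stands. The plan says 19 is sufficient, not that it is the minimum, and uses the same number for several endpoints. If an endpoint needed only 15 per group, power at 19 with alpha 0.05/3 would be 77%; if 13, it would be 84%. The documents therefore do not show that a split must cost the planned power.
- **The microbiota is a secondary objective.** Also true. It belongs in a separate, exploratory family and carries less weight here.

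A reader might also infer that four primary objectives and three primary endpoints contradict each other. They do not: the second list merges two bullets of the first, and the content is the same.

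**Conclusion.** The concern holds as a gap that is cheap to close. As written, one unadjusted 0.05 rule covers at least 11 unranked primary analytes and an open-ended peptide panel. The chance of at least one false positive is 43% for 11 independent tests and about 18-37% at assumed correlations of 0.3 to 0.8. Counted as three or four endpoints, it is 14% or 19% under independence and about 10-17% with correlation. These figures assume one test per item and no true differences.

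They do not mean that several false findings are to be expected: the expected number is 0.55 at 11 tests and would reach three only at 60 (0.05 × 60). The power figures are conditional on d = 0.934, or on d = 1.145 if the 13 participants are per group. Family sizes and correlations are not in the documents.

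**What to change.** 1. Prespecify one lead endpoint at 0.05, with one named between-group test, from those the trial was sized on (circulating BCM-7 or urinary lactose). Otherwise state that no confirmatory claim is made. The choice must be made before the data are seen.
2. For the remaining primary analytes, prespecify one between-group P value each and apply Benjamini-Hochberg at q<0.05 in two families: (a) urinary lactose (unless it is the lead), hormones and endocannabinoids; (b) the peptide panel. Say that error is controlled per family, not over all families.
3. Apply Benjamini-Hochberg separately to the microbiota correlations and label them exploratory.
4. Report PLS-DA separation only with cross-validation and a permutation P value.
5. State in Sample size calculation that the 80% power is per endpoint, before multiplicity adjustment.

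The primary lists in Objectives and Sample size calculation need no change.

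**Cost.** SAP wording, one adjustment call in R per family, and the PLS-DA validation runs; no more subjects. There will be fewer nominally significant results and lower power per analyte, as tabulated in the working.

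Separate families keep the result for lactose, hormones and endocannabinoids from depending on the peptide panel, but they do not always give more power. With one of ten family (a) analytes differing (d = 0.934, 19 per group), separate-family power is 47%. Pooled with 30 peptides it would be about 50% if 8 peptides differ and about 60% if 15 do. Pooling lowers power only if few peptides differ.

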### *Continuous variables with repeated measures*

Normality of measures, for each time, will be assessed using the Shapiro-Wilk test.

Differences of variables between baseline and over time within and between the groups, for normally distributed variables, will be tested by ANOVA with repeated measures on one factor (time) and Bonferroni adjustment for multiple comparisons. For non-normally distributed variables, Friedman test and pairwise Wilcoxon as a *post hoc* test will be applied.

Analysis of quartiles will be performed for both baseline values and pairwise time points ( $\Delta$ ) upon milk ingestion.

For these variables with repeated measures, the total area under the curves (AUCs) will be also estimated using the linear trapezoidal rule, and differences in AUCs between the groups will be assessed by proper parametric or non-parametric analyses including as covariates the potential confounding variables measured at baseline.

Pearson's correlation coefficients will be calculated to assess bivariate associations among continuous variables at baseline or partial associations of estimated AUCs controlling for baseline values for variables with repeated measures.

Spearman's rank correlation will be used to assess association between non-parametric variables collected and microbiota related variables (e. g. species abundance and genes abundance).

In order to explore differences in microbiome profiles, a Partial Least Squares Discriminant Analysis was applied.

Furthermore, principal component analyses (PCA) on specific variables at baseline or unstandardised residuals correlation between AUCs and related baseline values will be also performed in order to extract features relevant to the cluster structure. Moreover, statistical significance of the distance between groups in the PCA analysis will be computed using the Hotelling T2 test.

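### The repeated-measures ANOVA of the six-draw plasma profiles has no sphericity correction, so its time and group-by-time tests are probably too liberal, and no rule says what happens to a subject with a missed draw

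*Combined protocol and SAP*

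**What the plan says.** Under Milk test, the protocol schedules a baseline blood sample at time 0 and further samples at 0.5, 1, 2, 4 and 6 hours after the milk, six in all.

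Under Continuous variables with repeated measures, the SAP tests normally distributed variables within and between groups by "ANOVA with repeated measures on one factor (time) and Bonferroni adjustment for multiple comparisons". It continues: "For non-normally distributed variables, Friedman test and pairwise Wilcoxon" as the post hoc test. It also plans a between-group comparison of total AUC by the linear trapezoidal rule, with baseline covariates.

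Under Statistical analysis, the rules are "Two-tailed P values lower than 0.05 were considered significantly different" and, for missing data, "no imputation of missing data will be performed".

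Under Sample size calculation, 19 per group gives 80% power for a 40% difference in BCM-7, and then: "The participant number will be increased up to 40 (20 subjects per group) in view of possible dropouts".

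Nowhere does the plan name a sphericity test, an epsilon correction, a covariance structure, a missing-data assumption, or a rule for a subject with some but not all draws.

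**The concern.** Two gaps meet in the same analysis.

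**Sphericity.** The ordinary F tests for time and group-by-time are valid only if the differences between every pair of time points have the same variance. Here the intervals run from 0.5 to 2 h around a postprandial peak. Neighbouring samples will usually correlate more strongly than distant ones, and spread usually grows near the peak. Either feature breaks the assumption and makes the F tests reject too often. Group-by-time is the test of whether the postprandial profile differs between habitual and non-habitual milk consumers, which is what the primary plasma objectives ask.

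**Incomplete subjects.** The classical ANOVA layout and the Friedman test both need every time point. A trapezoidal AUC needs every point too, or an interpolation rule that the plan does not give. With no imputation and no stated rule, a single failed draw or assay could remove a subject, and the enrolment margin is one subject per group. The choice to drop or keep such subjects would also be left until after the data are seen.

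**Working it through.** **Inputs from the documents.** Six times (0, 0.5, 1, 2, 4, 6 h); 20 enrolled and 19 required per group; two-sided 5% level; 80% power.

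**Inputs assumed.** The covariance between draws, the missing rate per draw, and independence of misses across draws. The documents give none of these.

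**The plan's own figure.** The 19 per group cannot be reproduced, because the SD for BCM-7 is only in the cited study. Solved backwards with a two-sample t test, 19 per group at 80% power implies a standardised difference d = 0.934, that is an SD of 40% / 0.934 = 42.8% of the mean. The allowance is 19 / 0.95 = 20, a margin of 5%.

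**Step 1: type I error of the group-by-time test.** Null data were simulated with 20 per group at the six times. The uncorrected test refers F to 5 and 5 × 38 = 190 degrees of freedom. Greenhouse-Geisser multiplies both by the estimated epsilon. Serial correlation is per hour, so two draws h hours apart correlate as ρ^h.

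| Assumed covariance | Epsilon | Uncorrected F | Greenhouse-Geisser |
|---|---|---|---|
| Equal correlation 0.5, equal SDs (sphericity holds) | 1.00 | 5.05% | 4.3% |
| Serial 0.5 per hour | 0.73 | 6.8% | 4.6% |
| Serial 0.8 per hour | 0.52 | 8.8% | 4.9% |
| Serial 0.8, larger SD at the peak | 0.48 | 9.2% | 5.1% |
| Serial 0.8, much larger SD at the peak | 0.35 | 11.0% | 5.1% |

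Each figure rests on 10,000 runs, except the 9.2%, which rests on 40,000. With serial correlation 0.9 per hour and equal SDs, a separate simulation of 20,000 runs gave 9.3% uncorrected. The time test behaves like the group-by-time test (6.6% to 10.5% when sphericity fails). The between-group main effect stays at 4.8% to 5.3%. A test with unstructured covariance holds 4.9% to 5.2%.

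**Step 2: does any mixed model repair this?** No. On 60 complete simulated data sets, a random-intercept model gave the same group-by-time F as the uncorrected ANOVA (largest relative difference 1.4 × 10⁻⁵). It assumes the same equal correlations.

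**Step 3: complete subjects.** With independent misses at rate p per draw, the share complete is (1 − p)^6.

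| p per draw | Share complete | Complete per group of 20 | Power at d = 0.934 |
|---|---|---|---|
| 1% | 0.942 | 18.8 | 80% |
| 2% | 0.886 | 17.7 | 77% |
| 5% | 0.735 | 14.7 | 69% |

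For comparison, power is 82% with all 20 and 80% with 19. The one-subject margin is used up, in expectation, at p = 1 − 0.95^(1/6) = 0.85%. The power column is a two-sample t proxy for BCM-7. It is not the power of the group-by-time F test.

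**Step 4: clustered misses.** All draws fall in one visit, so misses may cluster. With a within-subject correlation of 0.5 (beta-binomial, assumed), the share complete is the product of (1 − p + i)/(1 + i) for i = 0 to 5. That leaves 19.5, 19.0 and 17.7 per group at 1%, 2% and 5%.

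**The case against.** **Deletion is not stated.** A reader might infer that the plan drops every subject who misses a draw. It does not say so. It rules out imputation and is silent on partly observed subjects, and a long-format ANOVA with a subject error term need not delete them. This stands: the documents support an unspecified rule, not deletion.

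**The power loss is narrower than it looks.** The SAP bases GI hormones and endocannabinoids on 13 participants, and even 5% missing per draw leaves 14.7 per group. The other 19-per-group calculation concerns urinary lactose and breath hydrogen, not blood draws. This stands: among the blood measures, the margin argument applies to BCM-7 only. At 1% to 2% missing the loss is small, and clustering makes it smaller.

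**Failure of sphericity is not demonstrated.** No figure in the documents shows it, and the AUC comparison uses one value per subject, so sphericity does not arise there. Both are correct. The inflation is likely, not proven, and is limited to the time and group-by-time tests. That is still reason to specify the correction in advance, because it costs little when sphericity holds (4.3% in the first row of the Step 1 table).

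**A mixed model as a cure-all.** It is tempting to say that any mixed model solves both problems. Step 2 shows otherwise. An unstructured covariance for six times also has 6 × 7 / 2 = 21 parameters, to be estimated from 40 subjects. Nor does the model replace the Friedman and Wilcoxon branch.

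**Conclusion.** The point holds in a limited form. As written, the ANOVA would probably give time and group-by-time p values that are too small: about 7% to 11% false positives at a nominal 5%, if serial correlation is between 0.5 and 0.9 per hour, with or without a larger SD at the peak. Greenhouse-Geisser brings this back to about 5%.

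The loss of subjects is conditional on a complete-subject analysis and on assumed missing rates. It is minor at 1% to 2% per draw. At 5% with independent misses it matters, with BCM-7 power near 69% by the t proxy. What is certain is that the plan leaves the handling of partly observed subjects open. Nothing here shows that 19 per group is wrong. The change should be made before analysis.

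**What to change.** For normally distributed or successfully transformed repeated measures, replace the ANOVA with a linear mixed model:

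- fixed effects for group, time as a category, and group-by-time;
- unstructured covariance with Kenward-Roger degrees of freedom;
- a fallback covariance named in advance in case of non-convergence, not a random intercept alone and not chosen by best fit after the data are seen;
- all available draws used, with no imputation, and the missing-at-random assumption stated;
- the between-group AUC contrast estimated from the model, so that it also uses partly observed subjects;
- Bonferroni kept for the time-point contrasts.

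If the ANOVA is kept, report Greenhouse-Geisser-corrected p values for time and group-by-time. In either case, state how partly observed subjects enter any ANOVA, Friedman or trapezoidal AUC analysis that remains.

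The cost is SAP wording and minor extra analysis work in R, with no new data. The downsides are slightly less favourable p values and 21 covariance parameters to estimate from 40 subjects.
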